In the HIV population, a single study has examined the effect of treatment of depression on self-reported cognitive difficulties and performance on neuropsychological tests, as part of a randomized controlled trial of antidepressant efficacy [10]. Following 12 weeks of antidepressant treatment, HIV+ individuals who reported a decrease in depressive symptoms also reported significantly fewer cognitive difficulties, despite an absence of improvement on neuropsychological testing.

In the context where the use of questionnaires eliciting cognitive difficulties is suggested as a first-line screening for HIV-Associated Neurocognitive Disorder [11], it is important to document the clinical factors that influence these self-reports in order to inform their clinical interpretation and develop interventions for individuals reporting cognitive difficulties.

Understanding and Optimizing Brain Health Now (BHN) cohort study: Cohort participants (N=840) are studied prospectively over a 27-month period with visits every 9 months. Patients complete questionnaires on mood (Hospital Anxiety Depression Scale-HADS), presence of cognitive symptoms (Patient Deficit Questionnaire-PDQ), and a computer-based evaluation of cognitive ability (B-CAM) [12].

Computerized Cognitive-Behavioral Therapy (cCBT): A number of computerized treatment programs have been developed to address symptoms of depression and anxiety, and several meta-analyses of randomized controlled trials (RCTs) have shown evidence for their effectiveness [13, 14]. One such program, Good Days Ahead, teaches the basic principles of CBT in nine therapy sessions, each typically taking 30 minutes to complete. Good Days Ahead has been found to be as effective as face-to-face CBT in decreasing symptoms of depression and anxiety [15]. Patients receiving treatment delivered by a computer can be provided with different levels of guidance and support: self-guidance, guidance by a technician who sends reminders, or guidance by a clinician [13]. A recent meta-analysis of cCBT for depression and anxiety has shown that the treatment delivered with no guidance or support yielded, on average, a smaller effect size (Cohen's $d = 0.17$) than cCBT delivered with at least one hour of knowledgeable assistance during the course of therapy (Cohen's $d = 0.72$) [15]. Offering some assistance thus appears to be necessary for achieving better therapy outcomes.

STUDY OBJECTIVES

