underlying platform generates customized learning experiences for each individual user with content including videos, text, quizzes and interactive exercises. The program comprises nine lessons of 30 minute each during which the user first learns the key concepts; then applies them to the program's main character who suffers from depression; and then applies those techniques to their own personal challenges (<http://www.empower-interactive.com/solutions/good-days-ahead>). Participants are expected to complete the nine sessions over 9-12 weeks.

As patients complete the cCBT program, their progress will be monitored by the research coordinator through a secure web site, using the program's dashboard feature that includes tracking of mood ratings, exercises, comprehension and completion rates. Participants will receive guidance during regular contacts by a trained research coordinator knowledgeable about the program and the basics of CBT.

MEASUREMENT

Three types of measures are under study: (i) depressive symptoms, (ii) self-reported cognitive difficulties; (ii) cognitive performance.

(i) Depressive symptoms will be measured using the Hospital Anxiety and Depression Scale (HADS) [19] before beginning and right after cCBT completion. It comprises two 7-item scales designed to rate depression and anxiety. It was developed to be brief, non-threatening and to exclude items which might reflect somatic symptoms. It has been widely used in research [20]. A score on the depression subscale (HADS-D) ≥ 8 is indicative of the presence of depression.

(ii) Self-reported cognitive difficulties will be measured using the C3Q collected before beginning and right after cCBT completion. The C3Q is a self-report measure of cognitive difficulties comprised of 18 items covering multiple cognitive domains. For each item, individuals rate the frequency of a cognitive difficulty on a three-point scale. The items fit the Rasch model, producing a legitimate total score with mathematical properties ranging from 0-36 with lower scores indicating more severe difficulties. C3Q has good content and construct validity and a good internal reliability (Person Separation Index 0.84) [18]. The mean score of C3Q among HIV+ individuals is 26.3 (SD: 8.2).

(iii) Cognitive performance will be measured by the B-CAM, a computerized test of cognition that yields a score on a continuous metric [21]. The B-CAM is administered at the regular BHN

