The Effects of computerized Cognitive Behavior Therapy (cCBT) on Brain Health: A feasibility study

cohort visits. Two values will be used, those closest to the beginning and end of the CBT intervention period, usually 9 months apart.

STATISTICAL ANALYSIS AND SAMPLE SIZE

Basic descriptive statistics will be used to characterize the participants including values on all the outcomes.

To meet the first aim of linking change in depressive symptoms (as a result of cCBT) to change in self-reported cognitive difficulties, an analysis based on a comparison of two means will be carried out. The cCBT cohort will be classified as having changed on depressive symptoms if the score on the HADS-D has either fallen to below 8 or decreased by $\frac{1}{2}$ SD (2 points). The mean value of change on the C3Q will be compared between these two groups (depression improved vs no change), using an adjusted t-test based on linear regression, adjusted for covariates that differ between the two groups. This t-test is an estimate of between group effect size. The parameter of interest, however, is the within group effect size for cognitive change using the standardized response mean (SRM), which is the average within group change divided by the standard deviation of change. The two SRMs will be compared using relative effectiveness: SRM (depression improved group) / SRM (depression no change group)[16]. If this ratio exceeds 1.0, there is supportive evidence for a greater response in the depression improved group. This information on the between and within-effect sizes will be used to develop a fully powered study of this association.

The extent to which changes in self-reports are concordant with changes in cognitive performance will be assessed using percent agreement and 95% confidence intervals (CI). Each person will be classified as a responder or not based on change on the C3Q and on the B-CAM, with responder status defined as improvement of $\frac{1}{2}$ SD. This represents a change of 4 points on the C3Q and 2.3 points for the B-CAM. The table below shows the potential outcome patterns. If the value of c=0, all persons with decreased reports of cognitive difficulties also had improved cognitive performance with cCBT.

The Effects of computerized Cognitive Behavior Therapy (cCBT) on Brain Health: A feasibility study

		Cognitive difficulties C3Q	
		Decreased	no change
Cognitive performance B-CAM	improved	a	b
	no change	c	d

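### Aim 2 pairs a 9-12 week change in C3Q with a B-CAM change over usually 9 months, so disagreement between them can come from timing alone

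*Combined protocol and SAP*

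**What the plan says.** The section MEASUREMENT gives the two cognitive measures different timetables. On self-report: "Self-reported cognitive difficulties will be measured using the C3Q collected before beginning and right after cCBT completion". The section on the intervention sets the length of that window: "Participants are expected to complete the nine sessions over 9-12 weeks".

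Cognitive performance is not measured for this sub-study. "The B-CAM is administered at the regular BHN" cohort visits, and the plan borrows from them: "Two values will be used, those closest to the beginning and end of the CBT intervention period, usually 9 months apart". This fits the visit schedule in BACKGROUND: "Cohort participants (N=840) are studied prospectively over a 27-month period with visits every 9 months". The same paragraph lists what cohort participants complete, including "presence of cognitive symptoms (Patient Deficit Questionnaire-PDQ), and a computer-based evaluation of cognitive ability (B-CAM"). Self-report by PDQ and performance by B-CAM thus belong to the same cohort assessments. In this sub-study the PDQ is used only for entry (a score of at least 30).

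Under STATISTICAL ANALYSIS AND SAMPLE SIZE, each person is a responder or not on each measure, at half an SD (4 points on the C3Q, 2.3 on the B-CAM). Concordance "will be assessed using percent agreement and 95% confidence intervals (CI"). A zero in cell c is read as showing that everyone whose reported difficulties fell also performed better under cCBT. The plan discloses the 9-month spacing. It gives no maximum lag, no lag reporting, no sensitivity analysis and no caution about reading the cells.

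**The concern.** The second hypothesis is about individuals: those who improve on self-report should improve on performance, and those who do not should not. A 2x2 table of responders tests this only if both changes describe the same period. Here the C3Q sees the therapy weeks, and the B-CAM also sees whatever happens in the months before and after. A person who improves during cCBT and slips back before the next cohort visit lands in cell c. A person who improves only outside the C3Q window lands in cell b. Neither shows that self-report and performance diverge.

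Two planned outputs are affected: the percent agreement, and the comparison of characteristics between concordant and non-concordant people, into which anyone misplaced by timing is carried.

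**Working it through.** **The plan's own figure.** For 12 of 30, the Wilson interval has centre (0.40 + 3.8416/60)/(1 + 3.8416/30) = 0.4640/1.1281 = 0.411. Its half-width is 1.96 × √(0.40 × 0.60/30 + 3.8416/3600)/1.1281 = 0.165. The result is 0.246 to 0.577, which reproduces the stated 0.25 to 0.58. This interval covers sampling error only, not the difference in windows.

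**Overlap of the windows.** Take 9 months as 39 weeks and assume the two visits bracket therapy. Then 9/39 = 23% and 12/39 = 31% of the B-CAM interval is covered by the C3Q. The remaining 27-30 weeks, 69%-77%, are not.

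**Error-free, perfect tracking.** Let one latent score drive both measures, so that same-window agreement is 100% by construction. Assumptions not in the documents: a random walk with a 9-month SD of change of 0.5 to 1.0 SD, and a mean gain during therapy of 0 or 0.5 SD, kept afterwards. The responder threshold is 0.5 SD, as in the plan.

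- With a gain of 0.5 SD the threshold equals the mean change, so agreement = 1/2 + arcsin(√f)/π, where f is the share of overlap. For f = 9/39: 0.5 + 0.501/3.142 = 0.659. For f = 12/39: 0.5 + 0.588/3.142 = 0.687. Half of the disagreement falls in cell c: (1 − 0.659)/2 = 0.17, or about 5 of 30 people.
- Simulation over the whole range (1 million draws per setting) gives agreement 0.66-0.85 and kappa 0.09-0.37. The highest agreement occurs where few people respond on either measure, so it is not reassuring.
- A different model (39-week latent correlation 0.5-0.9; gain 0, 0.3 or 0.5 SD; none, half or all of it kept at the next visit) gives agreement 0.58-0.87, with 31%-79% of C3Q responders in cell c.

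**With measurement error.** MEASUREMENT gives the C3Q a Person Separation Index of 0.84. Assume the same reliability for the B-CAM, so that each score has error variance 1 − 0.84 = 0.16. For the random walk and a 12-week window:

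| Windows | Agreement |
|---|---|
| As planned | 55%-67% |
| Both over therapy | 56%-73% |
| Both over 9 months | 64%-80% |

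Setting by setting, the planned windows lose about 1-7 points against a shared therapy window and 5-16 against a shared 9-month window. A 9-week window raises the last figure to about 18. For example, take gain 0.5 SD and 9-month SD of change 1, with true-score SD 1 and hence error variance 0.16/0.84 = 0.19 per score:

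- Planned: ρ = 0.231/√((0.231 + 0.381) × 1.381) = 0.251, so agreement is 0.5 + 0.254/3.142 = 0.581.
- Shared 9 months: ρ = 1/1.381 = 0.724, so agreement is 0.5 + 0.810/3.142 = 0.758.
- The loss is 0.177. Using 0.16 for the error variance instead moves it by about one point.

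**What PDQ selection would do.** Assume no true change, reliability 0.84, and an entry cut-off 0 to 1 SD above the cohort mean. Among unselected people, the chance of a half-SD improvement is P(Z > 0.5/√(2 × 0.16)) = P(Z > 0.88) = 19%. Among those selected on the same PDQ score, simulation gives 25%-32%. At reliability 0.70 the figures are 26% and 36%-48%.

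**The case against.** The case against is substantial, and much of it stands.

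- **The 100% comparison is a best case.** A reader might infer that timing costs the trial 15-34 points of agreement. That contrast requires error-free measures, and the plan's own reliability figure rules this out for the C3Q. With error on both measures the loss is much smaller, and at n = 30 the plan's interval already runs from 0.25 to 0.58.
- **Drift may be modest.** The POPULATION section requires a stable HAART regimen and no expected medication changes that could affect mood or cognition. The assumed random-walk SDs have no source in the documents.
- **The aim is secondary and exploratory.** It has no test and no decision threshold, and the 9-month gap is disclosed. A reader might infer that the trial will report that self-report does not match performance. The plan commits to no such conclusion.
- **PDQ is not a clean replacement.** A reader might infer that a same-interval PDQ table should become the main analysis. The documents do not support that. Aim 2 concerns change in people treated with cCBT, and most of a PDQ change would lie outside therapy. Aim 1 uses the C3Q. A PDQ of at least 30 is also an entry criterion, and the online eligibility check repeats the HADS and uses the C3Q, not the PDQ. If the qualifying visit is also the baseline visit, regression to the mean would inflate PDQ responders and cell c. The C3Q has no stated entry cut-off.

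What does not stand is that disclosure is enough. Stating the gap does not change how the plan reads the table. In the other direction, 9-12 weeks is an expected duration and the first C3Q is completed at eligibility confirmation, so the C3Q window may be somewhat longer; nothing suggests it approaches 9 months.

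**Conclusion.** The concern holds as a problem of interpretation. The mismatch is in the text, and no planned analysis deals with it. Different windows alone can fill cells b and c, so those cells cannot by themselves be read as discordance under cCBT.

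Only the direction is certain. The sizes rest on an assumed drift, an assumed gain, a B-CAM reliability that the documents do not give, and visits that bracket therapy. On those assumptions, timing costs about 1-7 points against a shared therapy window and about 5-18 against a shared 9-month window. The error-free range of 66%-85% illustrates the mechanism and does not forecast the trial's result. The documents do not support calling Aim 2 uninformative or moving its main table to the PDQ.

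**What to change.** 1. Keep the C3Q/B-CAM table as the main Aim 2 analysis.
2. Amend STATISTICAL ANALYSIS AND SAMPLE SIZE so that cells b and c are not read as discordance under cCBT where the two windows differ.
3. Report, for each participant, the days between each C3Q and its paired B-CAM.
4. Pre-specify a supporting concordance table of PDQ change against B-CAM change between the same two cohort visits, with PDQ responder status at half of the cohort PDQ SD.
5. State the limits of that table: the PDQ is a different instrument; its change includes time outside cCBT; and selection on a PDQ of at least 30 can inflate PDQ responders and cell c if the qualifying visit is the baseline visit.

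The cost is analysis work and wording. PDQ and B-CAM are already cohort assessments, so participants take on nothing new. The PDQ SD is not in the documents and must be taken from the cohort data and fixed before the table is produced.

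### Reading an SRM ratio above 1.0 as support for the first aim goes wrong when the no-change group's SRM is zero or negative, and no interval accompanies the ratio

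*Combined protocol and SAP*

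**What the plan says.** Study Objectives in the protocol asks how far a fall in depressive symptoms goes with fewer reported cognitive difficulties. Study Hypothesis words this in terms of people whose depressive symptoms are reduced.

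Statistical Analysis and Sample Size takes up the aim with the sentence opening "To meet the first aim of linking change in depressive symptoms (as a result of cCBT) to change in self-reported cognitive difficulties". Its steps are:

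- **Groups.** Participants are "classified as having changed on depressive symptoms if the score on the HADS-D has either fallen to below 8 or decreased by" half an SD, given as 2 points. All others, stable or worse, form the no-change group.
- **Between-group comparison.** Mean C3Q change is compared "using an adjusted t-test based on linear regression, adjusted for covariates that differ between the two groups".
- **Named parameter.** "The parameter of interest, however, is the within group effect size for cognitive change using the standardized response mean", defined as mean change divided by the SD of change.
- **Rule.** The SRM of the improved group is divided by that of the no-change group. "If this ratio exceeds 1.0, there is supportive evidence for a greater response in the depression improved group".
- **Use.** "This information on the between and within-effect sizes will be used to develop a fully powered study of this association".

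The Measurement section gives the C3Q a range of 0 to 36, "with lower scores indicating more severe difficulties". Improvement is therefore a positive change, and a group that declines has a negative SRM. The Protocol Summary plans for 30 completers. A 95% CI is planned only for percent agreement, under the second aim.

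**The concern.** A ratio of two effect sizes orders them correctly only if the denominator is positive. Here the denominator is the C3Q response of people whose depression did not improve. If cognition follows mood, as hypothesised, that response should be small, so in a group of 10 to 20 people the estimate will often be close to zero or below it. The rule then misreads the very pattern the study is looking for. Nothing in the section guards against this, and no interval shows how unstable the ratio is.

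The study is exploratory and makes no power claim. Even so, its stated reading of the first aim rests on this rule, and its effect sizes are meant to inform a later powered study. A false failure could discourage that study.

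**Working it through.** **The plan's own figures.** No numerical result or precision is stated for the first aim, so there is none to reproduce. The one precision figure in the document belongs to the second aim: 12/30 = 0.40 with 95% CI 0.25 to 0.58. A Wilson interval gives 0.246 to 0.577, which agrees.

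**Inputs.** From the documents: the ratio and the 1.0 threshold (Statistical Analysis and Sample Size), the C3Q direction (Measurement) and n = 30 completers (Protocol Summary). Assumed, because the documents do not give them: the true SRMs, the split of the 30 between groups, normally distributed change scores and, for power, two-sided 0.05.

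**Step 1: algebra.** Let S1 be the improved group's SRM and S2 the no-change group's.

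- If S2 > 0, S1/S2 > 1 means S1 > S2, as intended.
- If S2 < 0, S1/S2 > 1 means S1 < S2, the opposite.
- If S2 = 0, the ratio is undefined.

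The ratio is also unchanged when both signs are flipped, so it cannot tell two gains from two declines.

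**Step 2: worked cases** (15 per group). The interval uses SE = sqrt(1/n1 + S1²/(2(n1−1)) + 1/n2 + S2²/(2(n2−1))) and 1.96 × SE.

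| S1 | S2 | Ratio | Rule | S1 − S2 (95% CI) |
|---|---|---|---|---|
| 0.8 | −0.1 | −8.0 | not met | 0.90 (0.12 to 1.68) |
| −0.4 | −0.2 | 2.0 | met | −0.20 (−0.93 to 0.53) |

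For the first row, SE = sqrt(0.0667 + 0.0229 + 0.0667 + 0.0004) = 0.396 and 1.96 × 0.396 = 0.78. The interval for the difference lies wholly above zero, yet the rule reports no support.

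**Step 3: how often this happens.** Simulated studies, 200,000 or more per setting:

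| True S1, S2 | Split (improved/no change) | S1 larger in sample | Ratio > 1.0 | S2 ≤ 0 in sample |
|---|---|---|---|---|
| 0.5, 0 | 15/15 | 91% | 42% | 50% |
| 0.5, 0 | 20/10 | 89% | 39% | 50% |
| 0.8, 0.2 | 15/15 | 94% | 72% | 22% |
| 0.8, 0.2 | 20/10 | 92% | 65% | 26% |
| 0.8, 0.5 | 15/15 | 77% | 74% | about 3% |

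The shortfall between the third and fourth columns comes from samples with a non-positive denominator. At 0.8 and 0.2 (15/15) the ratio's central 95% range is about −36 to 39. At 0.5 and 0.5 (15/15) it is about −1.1 to 7.

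The opposite error, a pass with the improved group doing worse, occurs in at most about 0.4% of samples at 15/15 when the improved group truly gains. It is about 1% at 10/20 with SRMs of 0.5 and 0. It becomes common only if both groups truly decline: at −0.5 and −0.2 (15/15) the rule is met in 57% of samples, almost all of them false passes.

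**Step 4: the replacement.** The interval in Step 2 covers the true difference in about 94% of simulated studies, with a median half-width of about 0.75 to 0.85 at 15/15 and 20/10. For example, SRMs of 0.5 and 0 at 15/15 give 0.50 (−0.24 to 1.24).

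**Step 5: what a continuous analysis would add.** For a near-linear, near-normal relation, a 50/50 split keeps φ(0)²/(0.5 × 0.5) = 0.399²/0.25 = 64% of the information in HADS-D change. Take n = 30, a split at 2 points, and an assumed mean HADS-D change of 2 with SD 4. Power with continuous change against the split is then 62% against 41% at a correlation of 0.4, and 83% against 61% at 0.5. Adding both baselines to the continuous model gained 1 to 5 points in favourable settings. If baseline HADS-D correlates 0.5 in size with HADS-D change, the result ran from a loss of up to 10 points to about level.

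**The case against.** The strongest reply is that the section does not depend on the ratio. The regression-based t-test compares mean C3Q change directly and has no denominator problem. The between- and within-group effect sizes go forward to the later study, and the ratio is not named among them. Both SRMs must be computed before they can be divided, so a negative sign would be visible to the analyst. All of this stands, and it limits the harm. It does not rescue the rule: the plan names the SRM as its parameter of interest, states no interval for the t-test, and gives one reading for the ratio with no exception.

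It is also fair that the large gaps in Step 3 need a no-change SRM near zero. That is plausible under the hypothesis, but it is assumed.

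A reader might infer more than the documents support:

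- **That splitting HADS-D change is an error.** The hypothesis is worded in terms of groups, and an SRM per group needs groups. The split costs precision; it is not wrong.
- **That passing about 47% of the time with equal SRMs of 0.5 (15/15) shows a defect of the ratio.** The SRM difference is positive in 50% of the same cases. The figure shows only that an interval is missing.
- **That the covariate wording invalidates the comparison.** The section gives a criterion, namely difference between the groups, but no candidate list or threshold. Selecting on observed differences between groups formed after treatment is poor practice, but no size of harm has been shown.

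**Conclusion.** The point holds for the ratio rule. As written, it is reversed for a negative no-change SRM, undefined at zero, and unaccompanied by an interval. That much is arithmetic and needs no assumption.

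How often it would matter does rest on assumptions. With a true no-change SRM of 0 the rule misses about half of the studies in which the improved group did better; at 0.2 it misses roughly a quarter; at 0.5 it misses few. The practical risk is failing to recognise support, not declaring it falsely, unless both groups decline.

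The documents do not support the wider conclusion that the first-aim analysis as a whole is invalid. The group comparison is sound in form. The continuous slope is a worthwhile supplement, and the covariate list is a matter of missing detail. The rule should be changed before analysis, in proportion to an exploratory study of 30 people.

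**What to change.** 1. **Replace the 1.0 rule.** Report the difference in SRMs with a 95% CI, for example using the SE in Step 2, or the adjusted mean difference in C3Q change with its 95% CI, which the planned regression already yields. Give each SRM with a 95% CI, the two group sizes, and the number in the no-change group whose HADS-D worsened. Keep the ratio as descriptive only, and do not compute it when the no-change SRM is zero or negative.
2. **Add a supplementary slope.** Keep the improved versus no-change comparison. Alongside it, regress C3Q change (post minus pre) on HADS-D reduction (pre minus post) as a continuous variable, with baseline C3Q in the model, and report C3Q points per HADS-D point with a 95% CI. Show adjustment for baseline HADS-D as a sensitivity model; the figures in Step 5 do not justify making it mandatory.
3. **Fix the covariates in advance.** Choose them from a short list set before the data are seen, not by observed group differences. Baseline anxiety is one candidate already collected, since the HADS is described thus: "It comprises two 7-item scales designed to rate depression and anxiety". With 30 completers the list should stay at three or four.

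**Cost.** Only the analysis text changes, since HADS and C3Q are already collected before and after cCBT. The SRM difference will be imprecise, with a half-width of about 0.75 to 0.85, and the report should show this. The slope assumes linearity, which a plot can check.

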Among individuals with symptoms of depression who report cognitive difficulties and whose

The Effects of computerized Cognitive Behavior Therapy (cCBT) on Brain Health: A feasibility study

depression is treated with computerized Cognitive Behavioral Therapy (cCBT), to what extent is reduction in depressive symptoms associated with reduced reports of cognitive difficulties?

Secondarily, to what extent is the reduction in self-reported cognitive difficulties concordant with improvement cognitive performance?

STUDY HYPOTHESIS

The hypothesis is that people whose depressive symptoms are reduced following treatment with cCBT will also report fewer cognitive difficulties than before treatment. A second hypothesis is that changes in self-reported cognition will be concordant with changes in cognitive performance, such that people who make no improvement in self-report cognition will also show no improvement in cognitive performance and those who do improve on self-report will improve on cognitive performance.

STUDY DESIGN

This study is part of a larger project based upon a cohort multiple randomized controlled design [1]. Within a fully characterized cohort followed over time (n=840), people meeting the specific criteria for one or more interventions (here cCBT) are identified and a sample is randomly selected to receive the intervention. When the intervention is under investigation, the remaining eligible persons who do not receive the intervention serve as controls. In this study, we are not testing the effectiveness of cCBT as this has been demonstrated. Rather we are focusing on changes in cognition in relation to depressive symptoms mediated by cCBT. This study is an exploration of a hypothesis using a single cohort design with two repeated measures. For exploratory studies, an N of 30 optimizes an analysis based on means under the central limit theorem [16] .

POPULATION

Individuals who report depressive symptoms and self-reports of cognitive difficulties and who have agreed to be contacted for sub-studies will be invited to participate.

Inclusion criteria:

- Participant in the *Understanding and Optimizing Brain Health in HIV Now* (BHN) study

The Effects of computerized Cognitive Behavior Therapy (cCBT) on Brain Health: A feasibility study

- Able to communicate (understand and read) in English (Good Days Ahead software is only available in English)
- Score on the Hospital Anxiety and Depression Scale- depression subscale (HADS-D) ≥ 8

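### The first hypothesis is a within-group claim, but the plan gives the within-group change no confidence interval: its only test and only decision rule for this aim compare the two groups

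*Combined protocol and SAP*

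**What the plan says.** The Study Objectives section asks an association question: "to what extent is reduction in depressive symptoms associated with reduced reports of cognitive difficulties". The Study Hypothesis section makes a different kind of statement: "The hypothesis is that people whose depressive symptoms are reduced following treatment with cCBT will also report fewer cognitive difficulties than before treatment". The yardstick there is each person's own starting point, and no comparison group is mentioned.

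Under Statistical Analysis and Sample Size, participants are split by HADS-D change, and "The mean value of change on the C3Q will be compared between these two groups (depression improved vs no change". The method is a regression-based t-test that corrects for whichever characteristics turn out to be unbalanced. The plan describes the role of this test: "This t-test is an estimate of between group effect size". It then says: "The parameter of interest, however, is the within group effect size for cognitive change using the standardized response mean (SRM"). The two SRMs are combined by dividing the improved group's by the other group's. The rule for reading the result is: "If this ratio exceeds 1.0, there is supportive evidence for a greater response in the depression improved group". Both the between-group and the within-group effect sizes are to be carried into the design of a later powered study.

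The Measurement section scores the C3Q from 0 to 36, lower being worse, so a positive change (post minus pre) means fewer difficulties. The second aim is given 95% confidence intervals. The first aim is given none, and no alpha.

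**The concern.** Saying that a group moved from its own baseline is not the same as saying that it moved more than another group. Either can be true without the other. The plan's t-test and ratio both address the second statement, while the hypothesis makes the first. The SRM that bears directly on the hypothesis appears as a point estimate. With perhaps 10 to 20 people in the improved group, a point estimate alone does not show whether the change can be told apart from zero.

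The study could therefore end without a usable answer to its own first hypothesis. A ratio above 1.0 could also be quoted as support when neither group improved. As these effect sizes are meant to shape the next study, a misreading would carry forward.

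**Working it through.** **Inputs from the documents.** 30 analysed (Protocol Summary); C3Q SD 8.2 (Measurement); half-SD change on the C3Q of 4 points (Statistical Analysis), which reproduces as 8.2/2 = 4.1. No power, alpha or detectable effect is given for the first aim, so there is no planned figure to reproduce for it.

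**Assumptions.** Normal C3Q change with equal SD in both groups, two-sided 0.05, no covariates, improved/no-change splits as shown. Where points are used, SD of change = 8.2 × √(2(1 − r)): 8.2 at r = 0.5, and 8.2 × √0.6 = 6.35 at r = 0.7.

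**The three statements side by side.** Let μI and μN be the mean C3Q changes in the improved and no-change groups.
- Hypothesis: μI > 0.
- Null of the planned t-test: μI = μN.
- Decision rule: SRM(I)/SRM(N) > 1. With equal SDs this is μI/μN > 1, which ignores the sign of the two means.

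Two cases show what the ratio does. At μI = -0.5 and μN = -0.25 SD, the ratio is -0.5/-0.25 = 2, so the rule is met although both groups got worse. At μI = +0.5 and μN = -0.25, it is 0.5/-0.25 = -2, so the rule fails although the contrast is strong and in the hoped-for direction.

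**Simulated frequencies, 15/15 split.** Where two values are given, they are for SD 6.35 and SD 8.2.

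| True mean change (improved, no change) | Hypothesis | t-test favours improved | Ratio > 1 |
|---|---|---|---|
| +4, +4 points | true | 2.4% / 2.4% | 49% / 47% |
| +4, -2 points | true | 49% at SD 8.2 | 11% / 16% |
| 0, -4 points | false | 38% / 25% | not needed here |
| -0.5, -0.25 SD | false | under 1% | 58% |
| 0, 0 | false | 2.5% | 25% |

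In the second row the ratio is negative in 88% / 81% of trials, which is why the rule fails. In the fourth row, nearly all ratios above 1 arise with both observed means negative. The t-test and the ratio thus go wrong in different situations: the t-test when the no-change group worsens, the ratio when both groups worsen.

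The pattern is not peculiar to an even split. With both groups at +4, the t-test favours the improved group in 2.5% of trials at 20/10 and at 10/20. With -4 v -2 points, the ratio exceeds 1 in 50% to 71% across those two splits and both SDs.

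**What an interval on the within-group change would give.** Half-width = t(n−1) × SD/√n. At n = 15, 2.145 × 6.35/√15 = 3.5 points and 2.145 × 8.2/√15 = 4.5 points. The range runs from 3.0 (n = 20, SD 6.35) to 5.9 (n = 10, SD 8.2). At a true change of +4 points and n = 15, the interval lies above zero in 62% (SD 6.35) or 42% (SD 8.2) of trials, whatever happens in the other group.

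**What that interval cannot do.** Suppose scores drift upward by 0.3 SD for reasons unrelated to depression (an assumed size). The improved group's interval then lies above zero in 19%, 25% and 29% of trials at n = 15, 20 and 24. Equal drift in both groups leaves the between-group test at 2.5%.

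**The case against.** The strongest reply is that the analysis is introduced as serving the first aim, which is about association, and that a between-group contrast is the right tool for that. The ratio rule claims only a greater response in one group, which is the kind of conclusion such a contrast can give. The within-group SRM is named as the target and is carried forward, and since the paired t statistic equals SRM × √n, the information needed is nearly all there. The study calls itself exploratory and sets no alpha, so rejection rates at 0.05 use a threshold that the plan does not adopt.

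Most of this stands, and it rules out three stronger readings. A reader might infer that the plan ignores within-group change; it does not, as it estimates the change and omits only the inference. A reader might infer that a non-significant t-test will be counted against the hypothesis; nothing in the documents says so. A reader might also infer that a paired test in the improved group should become the sole criterion for support. That would be unsafe, because participants are selected on PDQ ≥ 30 and HADS-D ≥ 8, so regression to the mean is plausible, and the Background itself criticises before-and-after evaluation without a comparator.

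The objection does not remove the mismatch between the hypothesis as worded and the inference planned, nor the failure of the ratio rule when either SRM is negative.

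**Conclusion.** The point holds in a limited form. The plan estimates the quantity that its first hypothesis concerns but attaches no interval or comparison with zero to it, and its one test and one decision rule answer the association objective instead. With equal gains in both groups, the t-test favours the improved group in about 2.5% of trials although the hypothesis is true. With both groups worsening at -0.5 v -0.25 SD and a 15/15 split, the ratio exceeds 1 in about 58%; with no change in either group, it does so in 25%.

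The sizes rest on assumed splits, effects, SD of change and a 0.05 level. The logical gap between the hypothesis and the two between-group criteria does not depend on them. The figures should not be read as a finding that the study is underpowered or that the between-group comparison is wrong: tests of different nulls are not competing on power. In an exploratory study the consequence is a risk of misreading, which is worth correcting because the correction is cheap.

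**What to change.** In Statistical Analysis and Sample Size:

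- For each group, report the mean C3Q change (post minus pre) and the SRM, each with a 95% CI. Use the improved group's CI as the answer to the first hypothesis. Word it as change during cCBT, not change caused by it, and state regression to the mean as an alternative explanation.
- Keep the adjusted between-group difference, with its 95% CI, and label it as the answer to the association objective.
- Do not read an SRM ratio above 1.0 as support unless both SRMs are positive. Report the difference in SRMs with a CI instead.

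If the sponsor meant the first hypothesis as an association claim, reword the Study Hypothesis section to match the objective. That also resolves the mismatch, though the ratio rule still needs the change above.

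The cost is a few sentences and no new data. The downsides are one more interval per group and the need for cautious wording of an uncontrolled pre-post change.
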